9.4 RISK-BENEFITS

The selected dose range for study in TR03ext of 30 mg BID to 180 mg BID were chosen given the safety profile summarized in [Section 3.3.2](#) and discussed further in [Section 9.2](#) as well as detailed in the Investigator's Brochure. As summarized in, [Section 3.1.3.3](#), open label data from the TR01 study showed that pruritus suppression in the HD patients was noted with drug administration within the dose range that is planned for the current study.

Data obtained from a previous study in osteoarthritis patients dosed up to 180 mg BID with nalbuphine HCl ER tablets showed that objective opioid withdrawal symptoms at the termination of 3 weeks of therapy were absent or mild in degree (See the Investigator's Brochure Section 5.4.4.5 for details).

It should be noted that the commercially available nalbuphine HCl for Injection product in the United States (Nalbuphine HCl package insert) has a usual recommended dose of 10 mg for a 70 kg adult, administered subcutaneously, intramuscularly, or intravenously, which may be repeated every 3 to 6 hours as necessary (i.e., up to a daily dose of 40-80 mg IV); and, in non-tolerant individuals, the recommended single maximum dose is 20 mg, with a maximum total daily dose of 160 mg. Exposure following IV administration is approximately 6-fold higher than following oral administration (estimated oral bioavailability of nalbuphine HCl = 16%). Therefore, a 10-mg, 20-mg, or 160-mg IV dose would correspond to approximately 60 mg, 120 mg, and 960 mg oral nalbuphine, respectively. The highest dose proposed in the TR03 study is 180 mg BID (360 mg daily

dose), and this oral dose is well below the highest recommended daily treatment of 160 mg IV (equivalent to 960 mg oral) for the current marketed product.

The risk for patients participating in the study is judged to be low based on previous experience with nalbuphine oral tablets. In addition, in the current study, there will be a low initiation dose of 30 mg, a slow dose titration rate, and careful safety monitoring of patients during the clinical study.

There is no approved therapy for prurigo nodularis related pruritus in the United States or Europe. Should nalbuphine prove effective, patients with prurigo nodularis could potentially see benefit.

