Payne et al (1985) reported in a study of 46 subjects that the patients came from all social classes and racial groups, almost equally divided by gender and with a mean age of 39.5 years at the time of PN onset. Iking et al (2012) reported in their study that the patients were distributed in age between 11.9 years - 95.6 years with a median age of 61.9 years and there were more females than males affected by the disease.

Weigelt et al (2010) summarized the characteristic histological findings in PN that include the presence of thick compact orthohyperkeratosis; folliculosebaceous units in nonvolar skin in conjunction with a thick and compact cornified layer; irregular epidermal hyperplasia or pseudoepitheliomatous hyperplasia; focal parakeratosis; hypergranulosis; fibrosis of the papillary dermis with vertically arranged collagen fibers; increased number of fibroblasts and capillaries; a superficial, perivascular and/or interstitial inflammatory infiltrate of lymphocytes, macrophages and, to a lesser extent, eosinophils and neutrophils.

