In both genders, the most frequently reported adverse events were primarily in the Central Nervous System and Gastrointestinal organ system categories. A higher incidence of AEs was noted in females during week one of dosing with the gender asymmetry in AE generation lessening as a function of time. This difference in AE incidence may be related to the tendency of females to have higher plasma levels than males (about 1.7 and 1.3 fold higher for C_{max} and AUC, respectively). Nalbuphine total systemic clearance is reported to decrease with age leading to a higher absolute bioavailability (~ 44%) in elderly subjects (older than 65 years) relative to younger adults (11%) following oral administration (Jaillon, 1989).

In these eight clinical studies overall, the most frequently reported AEs in the single dose and multi-dose studies were CNS events, namely dizziness, headache, and somnolence. Gastrointestinal system AEs were mainly nausea and vomiting. Most of the AEs noted in the clinical study program were mild to moderate in severity.

In the case of single dose Phase 1 nalbuphine HCl ER tablet administration, there was a dose relationship to the incidence of AEs and there was minimal AEs observed at the 30 mg dose compared to initiating dosing at the higher doses. As a result, a titration to higher doses from a starting dose of 30 mg was selected for subsequent studies that also included TR01 in order to improve the tolerability of the drug.

Section 5 of the Investigator's Brochure summarizes the results of the clinical development program in detail.

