8.3 EXCLUSION CRITERIA

If a patient meets any of the following criteria, he or she is *not* eligible:

1. Patients with a history of congestive heart failure of Class 2 or higher as graded using the New York Heart Association scale (scale provided in [Appendix 5](#))
2. Patients with a history of angina pectoris grade 2 or higher as graded using the Canadian Cardiovascular Society grading scale (scale provided in [Appendix 5](#))
3. History of ventricular tachycardia, torsade de pointes, family history of sudden death, myocardial infarction or acute coronary syndrome within the previous 3 months, as reported by the patient.
4. Serum potassium below the laboratory lower limit of normality at the TR03 Visit 5. Note: Potassium levels below the laboratory lower limit of normal at Visit 6/Visit 1a should be repeated and potassium supplementation provided as appropriate.
5. QTcF interval >450ms on screening/Visit 1a ECG
6. Heart rate <50 BPM on any screening assessment. Patients with a resting heart rate of <50 bpm will have it repeated once after 5 minutes in the supine position, and if it remains <50 bpm during the repeat, they will be considered a screen failure
7. Use of a medication known to be associated with risk of torsade de pointes (see [Section 9.7.8](#), Safety Assessments, for hyperlink to the CredibleMeds Filtered QTDrug List for cardiovascular related prohibited medications with a known associated risk of Torsade de Pointes)
8. History of substance abuse within the past year as determined by the Investigator
9. Significant medical condition or other factors that in the opinion of the Investigator may interfere with the conduct of the study
10. Known hypersensitivity or allergy to nalbuphine or formulation components
11. Is a pregnant or lactating female.

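### Section 9.4 says the top oral dose is well below the injectable daily maximum, but the bioavailability the protocol reports for patients over 65 leaves almost no margin

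*Protocol*

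**What the plan says.** Section 9.4 (Risk-Benefits) cites the US label of the injectable product: "in non-tolerant individuals, the recommended single maximum dose is 20 mg, with a maximum total daily dose of 160 mg". It converts to oral doses with a single factor: "Exposure following IV administration is approximately 6-fold higher than following oral administration (estimated oral bioavailability of nalbuphine HCl = 16" per cent). From this, "a 10-mg, 20-mg, or 160-mg IV dose would correspond to approximately 60 mg, 120 mg, and 960 mg oral nalbuphine, respectively". The section takes 180 mg BID, 360 mg a day, as the highest dose and concludes that "this oral dose is well below the highest recommended daily treatment of 160 mg IV (equivalent to 960 mg oral"). No age group is distinguished. The paragraph attributes the 180 mg BID figure to TR03, but it is also the top of the TR03ext range given at the start of Section 9.4.

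Section 3.3.3 states that total clearance of nalbuphine falls with age, "leading to a higher absolute bioavailability (~ 44%) in elderly subjects (older than 65 years) relative to younger adults (11%) following oral administration".

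On who may enter, Sections 8.2 and 8.3 contain no age criterion. Age appears only in the definition of post-menopausal status. Entry requires completion of TR03. Section 3.1.1 describes a published prurigo nodularis cohort as "distributed in age between 11.9 years - 95.6 years with a median age of 61.9 years". Section 9.2 and Table 3 apply one titration range, up to 180 mg BID, to everyone treated.

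**The concern.** The protocol gives two accounts of how much of an oral dose reaches the circulation and uses only one of them for its safety margin. The account left out is the one for older patients. It is the less favourable of the two, and the cited cohort makes it likely that some participants will be over 65.

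An ethics committee or investigator reading Section 9.4 alone would take the margin as holding for every patient. The protocol names the central nervous system as the only target organ at high doses in animals (Sections 3.3.1 and 9.3). It also suggests, in Section 3.3.3, that higher plasma levels may explain the higher adverse-event incidence in women. Exposure therefore matters to the protocol's own safety reasoning, and a margin that depends on exposure should hold in the group with the highest reported bioavailability.

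**Working it through.** **Inputs**

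- Injectable daily maximum: 160 mg (Section 9.4).
- Highest oral daily dose: 2 × 180 = 360 mg (Section 9.4).
- Oral bioavailability F used for the margin: 16%, rounded to a 6-fold ratio (Section 9.4).
- F reported by age: about 44% over 65, 11% in younger adults (Section 3.3.3).

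**Formulas**

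- Oral equivalent of the IV maximum = 160 / F.
- IV equivalent of the top oral dose = 360 × F.
- Margin = 160 / (360 × F).

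**Reproducing the protocol's figure**

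160 × 6 = 960 mg oral, an exact match. Then 360 / 960 = 37.5% of the maximum, and 960 / 360 = 2.67-fold. Without rounding, 160 / 0.16 = 1000 mg and the margin is 2.78-fold. The small gap comes only from rounding 6.25 to 6.

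**Same calculation with other values of F**

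| F | Source | Oral equivalent of 160 mg IV | IV equivalent of 360 mg oral | Share of 160 mg | Margin |
|---|---|---|---|---|---|
| 11% | Section 3.3.3, younger adults | 1455 mg | 39.6 mg | 25% | 4.04 |
| 16% | Section 9.4, unrounded | 1000 mg | 57.6 mg | 36% | 2.78 |
| 40% | assumed lower end of about 44% | 400 mg | 144.0 mg | 90% | 1.11 |
| 44% | Section 3.3.3, over 65 | 364 mg | 158.4 mg | 99% | 1.01 |
| 48% | assumed upper end of about 44% | 333 mg | 172.8 mg | 108% | 0.93 |

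The margin is exactly 1 at F = 160 / 360 = 44.4%, practically the value reported for people over 65. The range of 40% to 48% is an assumption, made because the protocol gives 44% only as approximate. Nowhere in that range is 360 mg/day well below the maximum.

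**The case against.** The arithmetic in Section 9.4 is correct for the input it uses, and at exactly 44% the top dose is still nominally 1.6 mg/day under the maximum. The 44% comes from a cited oral pharmacokinetic study and may not carry over to an extended-release tablet. Titration is guided by tolerability and not forced, so only patients who reach 180 mg BID are concerned. Patients must have completed TR03, whose age criteria are not in this document. All of this stands and limits the point. None of it supports the unqualified statement, because the protocol reports the 44% without any caveat about formulation and never relates it to the 16%.

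A reader might infer more than the documents support:

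- **That the dose range and the low-risk judgement rest on this margin.** Section 9.4 bases the range on the safety profile in Sections 3.3.2 and 9.2 and the Investigator's Brochure. It bases the low-risk judgement on earlier tablet experience, a low starting dose, slow titration and monitoring. The injectable comparison is supporting context.
- **That a single 180 mg dose breaches the single-dose limit, which Section 9.4 equates to 120 mg oral.** The section claims a margin only for the daily total. An extended-release tablet taken about every 12 hours is not comparable with one injection that may be repeated every 3 to 6 hours.
- **That the 12.4-fold animal margin in Section 3.3.1 shrinks to about 3-fold.** That result, 12.4 / (44 / 11) = 3.1, takes 11% as its baseline. With 16%, the figure used in Section 9.4, it is 12.4 / (44 / 16) = 4.5. Section 3.3.1 derives the 12.4 from mean peak plasma levels, not from either bioavailability, and nothing shows that peak levels of this tablet scale with bioavailability.
- **That a particular number of the roughly 60 patients is affected.** A median and range from an external cohort do not give the proportion over 65 in this study, still less the proportion who reach the top dose.

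**Conclusion.** Wrong as written, within a limited scope. For patients over 65 who reach 180 mg BID, the protocol's own 44% turns a stated 2.67-fold daily margin into about 1.01-fold. The top dose is then 99% of the injectable daily maximum, or 90% to 108% over the assumed range of 40% to 48%. The margin is essentially removed rather than clearly exceeded.

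The conclusion assumes that the 44% applies to the extended-release tablet and that patients over 65 can enter. The TR03ext criteria do not exclude them, but a limit carried over from TR03 is possible. If either assumption fails, the protocol should say so, because as it stands Sections 3.3.3 and 9.4 are not reconciled. For younger adults the statement holds: at 11% the margin is wider than stated, at 4.04-fold.

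**What to change.** The sponsor should reconcile Sections 3.3.3 and 9.4. In Section 9.4, either restate the daily comparison by age group (at 44%, about 158 mg IV equivalent against 160 mg) or state why the 44% does not apply to the extended-release tablet. Withdraw the unqualified statement that the dose is well below the maximum, and state whether TR03 sets an upper age limit. Which dose or age rule is appropriate is for the sponsor to decide; none is proposed here. The cost is a few sentences of protocol text and a less favourable stated margin for one group.

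An inexpensive addition would be to summarise treatment-emergent adverse events, the events of special interest named in Section 9.3, and plasma concentrations by age (65 or under against over 65). Blood for pharmacokinetics is already drawn at every treatment visit, so no new data are needed. With at most about 60 patients the subgroups will be small and the summaries descriptive only. These tables could equally be specified in the SAP, and their absence from the protocol is not itself a fault.

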9.5 STUDY OVERVIEW

This is an open label safety and tolerability extension study for patients who have completed study TR03. Patients will either enter directly into the drug Treatment Period (Worst Itch NRS greater than or equal to 5 (≥ 5)) or enter an extended screening period of a no-drug Observation Period (Worst Itch NRS less than 5 (<5)) based on their reported NRS scores on the first Visit (Visit 1a). For up to 12 extended screening weeks, patients in the no-drug Observation Period may also transition into the drug Treatment Period if their Worst Itch NRS increases to greater than or equal to 5 (≥ 5).

The total study duration for any individual patient will be up to 53 weeks. For patients who enter directly into the Treatment Period, the total amount of time on drug will not exceed 50 weeks. For patients who enter the Treatment Period from the Observation Period, the total amount of time spent in the combined two periods of the study cannot exceed 50 weeks. All patients who received drug treatment will have a 2-week Washout and Safety Follow-up period at the end of the dosing period, unless consent is withdrawn.

The total amount of time in the Observation Period cannot exceed 12 weeks. After 12 extended screening weeks, patients not eligible for the Treatment Period are screen failed from the study. The study periods are summarized below in [Table 2](#).

Table 2: TR03ext Study Periods

Study Period	Study Weeks	Duration
Observation Period	
Patients who do not meet the criteria to start Treatment are followed in Observation Period visits for up to 12 extended screening weeks. During this time, the patient may meet criteria and become eligible to enter the Treatment Period. If the patient does not meet the criteria to enter the Treatment Period by the end of 12 extended screening weeks (OV12), participation in the study ends and the patient is screen failed.
	Up to 12 extended screening weeks
Treatment Period	
For patient directly entering the Treatment Period as of Visit 1a, the Treatment Period begins with Study Week 1 (Visit 1a) and ends with Study Week 50
 
For patients entering the Treatment Period after being followed in the Observation Period, the number of weeks on treatment and the end of the Treatment Period varies; Table 8 calculates the Treatment Visit assignments for any patient entering the Treatment Period from the respective Observation Period visits.
 
The End of Treatment Visit will take place after the patient completes the last week of study drug.
	Up to 50 weeks
Washout and Safety Follow-Up Period	
The Washout and Safety Follow-up Period is two (2) weeks in duration.
 
For patients directly entering the Treatment Period as of Visit 1a and completing 50 weeks of study drug treatment, the Washout and Safety Follow-up Period should take place during weeks 51 and 52.
 
For patients entering the Treatment Period after being followed in the Observation Period, the number of weeks on treatment and the end of the Treatment Period varies; Table 8 calculates the Treatment Visit assignments for any patient entering the Treatment Period from the respective Observation Period visits. The Washout and Safety Follow-up Period will take place during the two (2) weeks after the patients completes the last week of study drug.
 
The Washout and Safety Follow-up Period Visit will take place in the week following the completion of the two (2) week Washout and Safety Follow-up Period.
	2 weeks

9.6 STUDY PROCEDURES

Before the initiation of study-specific procedures the patient must be given a complete explanation of the purpose of the study, evaluations to be conducted, and risks/benefits for study participation. Patients must understand the requirements of the study, provide informed consent (See [Section 9.6.1](#) and [Section 20.3](#)), agree to the study restrictions, and agree to return for the required assessments. After review of the informed consent is documented, the patient must give written consent. For this study, patients will retain their study number from study TR03.

With the exception of Visits 1a and 1b, windows for all visits will be +/-3 Days. Please see the Schedule of Events in [Appendix 1](#) for details of the Titration Period assessments and the Study Schematics Flow Charts in [Appendix 2](#). See [Section 9.7.1](#) for details of Study Drug Dosing and [Section 9.7.6.4](#) for information on the use of pre-medications with the Study Drug. Visit 6 of TR03 will serve as TR03ext Visit 1a unless these visits do not occur on the same calendar day.

Visit 1a has procedures to be done as summarized in [Section 9.6.1](#) regardless of the patient's pruritus intensity score. Following a set of common procedures, only patients who qualify for the Treatment Period based on meeting the pruritus intensity criteria will be eligible to receive study drug; Visit 1a corresponds to TV1. For patients who, during the final visit of TR03, did not meet the pruritus intensity criteria to enter the TR03ext Treatment Period, Visit 1a corresponds to OV1, the first visit of the Observation Period. If during a subsequent observation period visit to the site, the patient meets the pruritus intensity criteria, then that observation visit immediately transitions into Visit 1b (it also corresponds to TV1 since it is now the first Treatment Period visit) – See [Section 9.6.3.3](#) and [Section 9.6.4](#).

For patients who transition to the Treatment Period from the Observation Period, [Table 8](#) provides details on the treatment visit schedule based on the study week that the patient transitioned from the Observation Period to the Treatment Period. The patient will follow the Treatment Visit schedule outlined on the Schedule of Events ([Appendix 1](#)).

For clarity,

Patients with a Worst Itch NRS greater than 5 (≥ 5) enter the Treatment Period and will receive Study Drug starting with an evening 30 mg dose (to be taken at home), after the Visit 1a (or Visit 1b) procedures have been completed.

Receipt of the first dose of study drug will define Day 1. Visit 1a or Visit 1b for these patients is also Treatment Visit 1 (TV1). Subsequent visits will be defined as TV2, TV3, etc.

Patients with a Worst Itch NRS less than 5 (<5) enter the Observation Period and will not receive study drug treatment. Visit 1a for these patients is also Observational Visit 1 (OV1). Subsequent visits will be defined as OV2, OV3, etc.

Patients in the observation period can be followed for up to 12 weeks.

If during the Observation Period, a patient's Worst Itch NRS increases to greater than or equal to 5 (≥ 5) and the patient meets all other eligibility criteria, Visit 1b procedures are to be performed. The patient's next visit will be Treatment Visit 2 (TV2). Do not repeat the Worst Itch NRS during Visit 1b.

If, however, at Observation Visit 12 the patient does not have a Worst Itch NRS greater than or equal to 5 (≥ 5), the patient will be screen failed without having initiated treatment with nalbuphine.

[Figure 2](#), [Figure 3](#) and [Figure 4](#) visually display the relationship between TR03ext study weeks, Treatment Period weeks and Observation Period weeks.

9.6.1 Visit 1a (Day 1 of Study Week 1)

See [Table 4](#) for summary of Visit 1a procedures. See [Section 20.3](#) regarding the informed consent process that must take place prior to any study procedures.

To the extent possible, the TR03 Visit 6 and Visit 1a should be performed on the same calendar day. In cases where this is not possible, the Investigator must contact the Medical Monitor prior to conducting Visit 1a to discuss which procedures are required to be repeated at the visit. All patients must complete Visit 1a within 30 days of their last dose of TR03 study drug in order to be eligible for study participation.

Study TR03 Visit 6 procedures in common with Study TR03 extension Visit 1a procedures do not have to be repeated unless the two visits do not occur on the same calendar day. The following procedures will be performed:

- obtain informed consent
- confirm eligibility
- obtain vital signs
- conduct a physical examination
- conduct a neurological exam
- collect central laboratory samples (hematology and chemistry)
- collect serum pregnancy sample in women of childbearing potential (regardless of sexual activity) and send for processing at the central laboratory*
- collect urine for central lab urinalysis
- collect urine for pregnancy test (regardless of sexual activity) and confirm negative results prior to dispensing study drug*

* If the urine pregnancy test result is negative and the serum pregnancy test result is positive, the patient is to be contacted and the following actions are to take place:

- instruct the patient to immediately discontinue taking study drug
- schedule the patient for an unscheduled visit to collect another serum pregnancy test

The serum pregnancy test result will be used to determine the patient's eligibility to continue receiving study treatment. See [Section 17.5.2.1](#) regarding how pregnancies are to be handled in this study.

- obtain blood for PK
- perform skin biopsy (optional procedure at select sites only). Obtain 3 samples (i.e., H&E, nerve fiber density (histology) and MOR/KOR density (histology, Western Blot)); see the Lab and Study Reference Manuals for details
- perform 12-Lead ECG after at least 5 minutes in a supine position (See the Study Reference Manual for ECG procedures, [Section 17.4](#) Electrocardiograms for the handling of Cardiovascular adverse events)
- record AEs
- review of concomitant medications, including over-the-counter medications, nutritional supplements, and vitamins; also collect the TR03 rescue medication log
- retrieve any remaining study drug from the parent study TR03
- administer the Worst itch NRS (paper version) and **review score for eligibility to either enter the Treatment Period or to continue in screening under the Observation Period**
 - a) If the Worst Itch NRS score is < 5 , start the Observation Period. Do NOT initiate study drug treatment at this visit
 - b) If Worst Itch NRS score is ≥ 5 , confirm eligibility and start the Treatment Period (see below, ‘For patients qualifying for drug Treatment Period only’).

The Worst Itch NRS (paper version) must be administered at the study site under the supervision of and by trained study staff, strictly adhering to PRO Administration Instructions (see Study Reference Manual)

For patients qualifying for the drug Treatment Period only (Visit 1a is also study visit TV1):

- complete PAS
- administer PRO measurements (paper versions):
 - Average itch intensity NRS
 - VRS
 - ItchyQoL
 - MOS Sleep-R
 - HADS
 - PBI-P

The PRO questionnaires must be administered at the study site under the supervision of and by trained study staff, strictly adhering to PRO Administration Instructions (see Study Reference Manual)

- perform skin biopsy (optional procedure at select sites only). Obtain 3 samples (i.e., H&E, nerve fiber density (histology) and MOR/KOR density (histology, Western Blot)); see the Lab and Study Reference Manuals for details
- dispense enough Study Drug to the patient for required dosing until their return at Treatment Visit 2, TV2
- dispense the Dosing Diary and instruct the patient on how to complete it
- dispense the TR03ext Rescue Medication Log and instruct the patient on how to complete it

- instruct patients to self-administer the first dose on the evening of Visit 1a at home
- instruct patients to notify the Investigator if any significant CNS AEs occur, and not to drive or operate dangerous machinery until the effect of the Study Drug can be assessed by the Investigator, see [Section 9.3](#)
- instruct the patient to take the Study Drug twice daily at approximately the same times of day. All patients should be instructed to titrate to their most tolerated dose. See [Table 3](#) Drug Dosing Schedule for more information. Here is the recommended Week 1 titration schedule for patients who tolerate study drug:

Day 1 (the first day that the patient receives a study drug dose): No dose in the AM and 30 mg in the PM

Day 2: No dose in the AM and 30 mg in the PM

Day 3: 30 mg in the AM and 30 mg in the PM

Day 4: 30 mg in the AM and 30 mg in the PM

Day 5: 30 mg in the AM and 60 mg in the PM

Day 6: 60 mg in the AM and 60 mg in the PM

Day 7: 60 mg in the AM and 60 mg in the PM

- instruct patients to bring all remaining Study Drug to the Investigator site for each study visit
- If a patient misses 3 or more consecutive doses, contact the Medical Monitor.

For patients starting the Treatment Period, the next visit will be TV2, Treatment Week 3.

For patients not qualifying for the drug Treatment Period only (Visit 1a is also study visit OV1), the patient will enter the Observation Period and the next visit will be OV2, Extending Screening Week 4. See [Section 9.6.3](#), Observation Period (Extended Screening Weeks 1-12).

